3. PLANNED ANALYSES

3.1. Final Analyses

The final planned primary analyses will be performed after the completion of the following sequential steps:

1. All participants have completed (or withdrawn from) the study as defined in the protocol.
2. All required database cleaning activities have been completed and final database release and database lock has been declared by Data Management.

4. ANALYSIS POPULATIONS

Population	Definition / Criteria	Analyses Evaluated
Safety analysis set	
• All randomised subjects who received at least one dose of HB-adMSCs infusion or placebo.• If participants receive a treatment different to their randomized treatment, they will be analysed according to the treatment actually received.	
• Safety• Study Population
Efficacy analysis set	
• All randomized participants who received all 5 infusions of HB-adMSCs or placebo.• Participants will be analysed according to their randomized treatment.	
• Efficacy

Protocol Number: HBCOVID02
 Hope Biosciences
 Statistical Analysis Plan

Confidential

Date: 14-Oct-2021
 Version: 1.0
 Status: Final

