Allogeneic HB-adMSCs to provide immune support against COVID-19.

- The patient develops a severe allergic reaction that occurs following investigational product administration.

A patient may voluntarily withdraw or be withdrawn from the study at any time for reasons including, but not limited to, the following:

- Patient withdrawal of consent: At any time, a patient's participation in the study may terminate at his/her request. The specific reason for patient withdrawal will be noted on the case report form (CRF).
- Lost to follow-up: The patient stops coming for visits, and study personnel is unable to contact the patient after repeated attempts (e.g., mail, or email).
- This study may be terminated at the discretion of the Sponsor or any regulatory agency.

If a patient's infusions are discontinued at any point during the trial and the patient maintains consent to contribute additional outcome information, the patient should continue to be followed through Week 26 for all safety and efficacy assessments. Investigators will be trained about the importance of retention and steps to prevent missing data.

The date and reason for withdrawal are to be documented in the CRF. The study site must immediately notify the medical monitor. The patients who withdraw prematurely must attend an early discontinuation visit if possible, at which time they will complete all assessments described in Table 2 under the Week 24 visit.

In the event that a patient discontinues prematurely from the study due to an Adverse Event (AE) or serious AE, the event will be followed until it resolves (returns to normal or baseline values) or stabilizes, or until it is judged by the Investigator to be no longer clinically significant. Once a patient is withdrawn from the study, the patient may not re-enter the study. If the subject develops symptoms associated with COVID-19 during the conduct of this study, they will be asked to consult their personal physician and be tested for COVID-19, and to self-quarantine for at least 14 days. Quarantine must occur while waiting for COVID-19 test results. Once asymptomatic, subject may resume site visits. If the test results are positive, the subject will be asked to quarantine and may continue to receive infusions at the quarantine site. If the subject develops severe symptoms (i.e., shortness of breath/difficulty breathing) they should go to the ER instead of personal physician.

Treatments

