Prior to commencement of any trial related activity, the investigator or designated staff will obtain written informed consent from the patient.

Patient Re-Screening

If a patient is screened and fails to meet any study entry criteria may be re-screened only once. Such patient must be fully consented a second time before the second set of screening assessments take place and shall be assigned a new subject number. Investigator discretion should be exercised in determining who may be re-screened.

In case of doubt about the accuracy of screening laboratory value(s), the laboratory test(s) may be repeated provided that this can be done within the 45-day screening period without the need to repeat all other screening procedures (i.e., no re-screening).

If a patient is enrolled after they have been re-screened, such subject shall be assigned a new subject ID number, different from the previous attempt to enroll.

Assessments by Week

Allogeneic HB-adMSCs to provide immune support against COVID-19.

Assessments will occur as outlined in the following subsections. For visits at Weeks 0 through 26, there will be a window of ± 4 days.

Screening

The Screening visit will last up to 45 days. These are the procedures to be performed during this visit:

- Demographic Information will be obtained.
- Medical History and Current conditions will be obtained,
- Concomitant Medications will be obtained. Every medication listed should match a condition in the medical history.
- Ascertain patient eligibility by evaluating patient results against the inclusion/exclusion criteria.

Upon completion of all Screening procedures, the Principal Investigator must confirm and document the patient eligibility in the “Screening Result” CRF and notify the Sponsor via Fax or e-mail.

Infusion Visits (Baseline/Week 0, Week 2, Week 6, Week 10, and Week 14)

Generally, these are the procedures to be performed at every infusion visit. For details, please refer to the schedule of assessments.

Baseline assessments will be taken before the administration of the first infusion. A second assessment of informed consent shall be obtained prior to the first infusion.

- Pre-infusion assessment will be made by telephone call in the morning prior to all infusion visits to assess any occurrence of symptoms. In the event a subject is exhibiting symptoms, the subject will be asked to remain home. ● Weight will be measured
- Vital Signs will be measured.

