5.5 General Considerations

Unless otherwise stated, all hypotheses will be tested at a 2-sided significance level of 0.05 and 95% confidence interval. All continuous measurements will be summarised descriptively at each visit by treatment using observed data.

Summary of continuous variables will be presented using N, Mean, Standard Error of mean (SE), Standard Deviation (SD), Median and Range (Minimum and Maximum). The categorical variables will be presented using number and percentage based on N.

For measurements over time mean values will be plotted to explore the trajectory over time. LOCF imputed data will be used as the basis for plotting data along with bars as standard error (SE) or Standard Deviation (SD), if not otherwise specified.

Primary endpoints of incidence of COVID-19 symptoms and Hospitalizations due to COVID-19 symptoms will be analysed based on binomial model and p-value will be displayed using two-sample binomial proportion test.

Additionally, time to first incidence of COVID-19 symptoms will analysed using Kaplan-Meir method.

A standard analysis of covariance (ANCOVA) model will be applied for secondary endpoints followed by Tukey's multiple comparison test to test the the significance of the effects of the treatment. The model includes treatment as fixed factor and the corresponding baseline value as a covariate.

Tukey's multiple comparison tests will be tested as two-sided hypotheses at a 5% level of significance. Treatment differences will be confirmed and considered significant if p-value reported is < 0.05 .

Protocol Number: HBCOVID02
Hope Biosciences
Statistical Analysis Plan

Confidential

Date: 14-Oct-2021
Version: 1.0
Status: Final

Presentation of results from a statistical analysis will include the estimated mean treatment effects (Least Square Means (LSMeans)) for absolute values and change from baseline. For all endpoints analysed statistically, estimated mean treatment differences will be presented together with two-sided 95% confidence intervals and p-values obtained using Tukey's method, and results from following paired comparisons will be displayed,

1. HB-adMSCs 200MM vs Placebo
2. HB-adMSCs 100MM vs Placebo
3. HB-adMSCs 50MM vs Placebo

All safety evaluations will be presented using Safety Analysis Set. The efficacy analysis will be presented using Efficacy analysis set.

Individual safety and efficacy parameters will be listed.

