6. STUDY POPULATION ANALYSES

6.1. Overview of Planned Study Population Analyses

The study population analyses will be based on the Safety analysis set.

Study population analyses including analyses of subject disposition, demographic and baseline characteristics, medical history, prior and concomitant medications. Additionally, including tobacco usage and alcoholic abuse.

A two sample binomial test will be applied for primary endpoints to calculate p-value comparing binomial proportions for incidence of COVID-19 symptoms and Hospitalizations due to COVID-19 symptoms.

p-value for treatment difference using one-way Analysis of variance (ANOVA) is displayed for baseline characteristics. A standard analysis of covariance (ANCOVA) model will be applied for secondary endpoints followed by Tukey's multiple comparison test to test the the significance of the effects of the treatment. The model includes treatment as fixed factor.

Details of the planned displays are presented in Appendix 5: List of Data Displays.

Categorical variables will be summarized by the number and percentage of subjects, and the continuous parameters will be summarized by n, mean, standard error of mean, median, sample standard deviation, minimum and maximum unless otherwise specified.

Disposition summary includes, subject screened, randomized and disposition at end of study – Week 26 along with reasons for withdrawals will be presented based on number of subjects and percentage. Subjects in different analysis populations also will be presented.

Protocol Number: HBCOVID02
Hope Biosciences
Statistical Analysis Plan

Confidential

Date: 14-Oct-2021
Version: 1.0
Status: Final

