7.1.3. Population of Interest

The primary efficacy analyses will be based on the efficacy analysis set population, unless otherwise specified.

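### The only efficacy set is limited to subjects who received all five infusions, so it is selected after randomization and a primary event before Week 14 can remove the subject who had it

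*SAP*

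**What the plan says.** SAP section 4 defines two sets. The safety set needs at least one infusion and is assigned to safety and study-population displays. The efficacy set is "All randomized participants who received all 5 infusions of HB-adMSCs or placebo", analysed by randomized arm. The protocol's Analysis Population section has the same five-infusion requirement, although its wording names only the cell product and, read literally, leaves out placebo subjects.

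The efficacy set then governs everything on efficacy. SAP 5.5: "The efficacy analysis will be presented using Efficacy analysis set". SAP 7.1.3: "The primary efficacy analyses will be based on the efficacy analysis set population, unless otherwise specified". SAP 7.2.3 does the same for the secondary endpoints, and the sensitivity ANCOVA and repeated-measures analysis in 7.2.4.1 use the set again. The Kaplan-Meier analysis of time to first symptoms sits under the general rule in 5.5.

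One passage points elsewhere. SAP 6.1 opens with "The study population analyses will be based on the Safety analysis set" and then says "A two sample binomial test will be applied for primary endpoints to calculate p-value comparing binomial proportions for incidence of COVID-19 symptoms".

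Infusions are due at Weeks 0, 2, 6, 10 and 14, with ±4-day windows (protocol Table 2). The primary endpoints run to Week 26 (SAP 7.1.1).

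**The concern.** Analysing subjects by randomized arm does not preserve the randomized comparison when entry to the set is decided up to 14 weeks later by treatment completion. Here the outcome itself can decide entry. On the morning of an infusion visit, "In the event a subject is exhibiting symptoms, the subject will be asked to remain home" (protocol, Infusion Visits). A subject who develops symptoms is asked to "be tested for COVID-19, and to self-quarantine for at least 14 days" (protocol, Withdrawal, Removal, and Replacement of Patients), which is longer than the 8 days that a ±4-day window spans. An infusion may also be held for an ongoing adverse event (protocol, Staggering). Reasons linked to the arm can remove subjects too, such as stopping treatment after a severe allergic reaction to the product.

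Removal is not automatic. The protocol adds "Once asymptomatic, subject may resume site visits" and allows infusions at the quarantine site after a positive test. No rule says whether an infusion given outside its window counts as received, so membership is undefined for the very subjects whose outcome matters most.

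At stake is the primary comparison, tested two-sided at 5% (SAP 2.3). The direction of bias is not fixed. Equal loss of cases dilutes a real difference, and unequal loss can create a false one in either direction. If the product increased COVID-19, the safety-set adverse-event summaries and DSMB review could still show it, but the primary efficacy comparison could miss it.

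**Working it through.** The plan has no figure of its own to reproduce here. The sample size of 53 is set by the number of banked and registered patients, with no event rate, effect size or power stated. The check is therefore an illustration under stated assumptions.

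**Inputs from the documents.** Last infusion Week 14; follow-up to Week 26; windows ±4 days; quarantine at least 14 days; 53 subjects at 3:1, so 53 × 0.75 = 39.75 and 53 × 0.25 = 13.25, taken as 40 active and 13 placebo; two-sided 5% two-sample proportion test.

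**Assumptions.** Constant hazard; 26-week risk p; a fraction q of subjects with an event before Week 14 miss an infusion and leave the set.

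**Step 1, how quarantine meets the schedule.** Take onsets uniform over days 0 to 98 and infusions due on days d = 14, 42, 70 and 98. A 14-day quarantine covers the whole window when onset falls from d − 10 to d − 4: 4 × 6/98 = 24.5% of onsets. For onsets up to the scheduled day, it ends after the window closes when onset falls from d − 10 to d: 4 × 10/98 = 40.8%. These are overlaps in time, not missed-infusion rates.

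**Step 2, risk seen in the five-infusion set.** Risk before Week 14 is e = 1 − (1 − p)^(14/26), which is 24.1% for p = 0.40 and 11.3% for p = 0.20. The risk among those kept is (p − qe)/(1 − qe). Example with q = 0.5: (0.400 − 0.120)/(1 − 0.120) = 0.318 and (0.200 − 0.057)/(1 − 0.057) = 0.152.

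**Step 3, a true effect with equal exclusion in both arms.** Power is by exact enumeration: the number excluded per arm is binomial, events among those kept are binomial, and the pooled z test is applied to each resulting table.

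| q | placebo | active | difference | ratio | power, 40 vs 13 |
|---|---|---|---|---|---|
| 0 | 40.0% | 20.0% | 20.0 points | 0.50 | 31.8% |
| 0.5 | 31.8% | 15.2% | 16.6 points | 0.48 | 26.8% |
| 1 | 21.0% | 9.8% | 11.2 points | 0.47 | 19.9% |

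The risk difference, which is the SAP's summary measure (7.1.2), shrinks. The risk ratio barely moves.

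**Step 4, no true effect.** Rejection rate of the same test, 40 vs 13, by the same enumeration:

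| risk in both arms | no exclusion | q = 0.5 in both | q = 0.5 active only | q = 0.5 placebo only |
|---|---|---|---|---|
| 40% | 5.1% | 5.1% | 9.3% | 7.1% |
| 20% | 4.8% | 4.1% | 8.3% | 4.1% |

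The false difference with q = 0.5 in one arm is 40.0 − 31.8 = 8.2 points at 40% risk and 20.0 − 15.2 = 4.8 points at 20%. It looks like benefit if the active arm loses the cases and like harm if placebo does.

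**The case against.** The definition is not in dispute. The objections are to its consequences.

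- **Inflated type I error needs exclusion to differ by arm.** Subjects and site staff are blinded, and the stay-home, quarantine and hold rules are the same in every arm. The one arm-linked route named, allergic reaction, is not tied to COVID-19 events. This stands: the one-arm figures are an extreme. With half of early cases lost on active and a quarter on placebo, the same enumeration gives 5.9% at 20% risk and 6.5% at 40%. Equal exclusion gives no inflation.
- **Hospitalization, the first-listed primary endpoint, is likely to be rarer than the risks illustrated.** If so, the inflation is smaller. At an assumed 5% risk, active-only exclusion moves rejection from 2.6% to 4.0%; at 10% it reaches 5.7%.
- **SAP 7.1.4.1 specifies each dose against placebo, about 13 vs 13.** There, one-arm exclusion gives 5.3% at 20% risk, and 7.7% at 40%, where the test already rejects 7.0% without exclusion. The extra rejections are few, but the false difference of 4.8 or 8.2 points is unchanged, because it does not depend on group size.
- **SAP 5.4 calls the tests exploratory, and this is a small Phase II trial.** That tempers the weight of a type I error argument. It does not justify an estimate from a selected set.
- **The list of displays (Appendix 5) is not in the text reviewed, and the mixed model in SAP 7.2.4.1 names no set.** A wider-set display could exist, but none is stated.
- **SAP 6.1 is closer to ambiguity than contradiction.** That is fair, but the primary population must still be unambiguous.
- **A late infusion may well count as received.** It may, and the plan should say so.

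None of this removes the selection after randomization or the dilution of a real effect under equal exclusion.

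**Conclusion.** The concern holds and should be corrected before unblinding. Every efficacy analysis with a stated population, apart from the unclear text in SAP 6.1, uses a set whose membership is settled up to Week 14 by treatment completion. The protocol gives real, though not automatic, routes from a primary event to a missed infusion. That follows from the text and needs no numerical assumption.

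The size cannot be known from the documents. The firmer part of the illustration is dilution, since equal exclusion needs no difference between arms. The false differences and raised rejection rates need exclusion to be unequal between arms and should be read as an upper-end illustration. All the figures rest on assumed risks, a constant hazard and an assumed share of early cases lost.

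**What to change.** In SAP section 4 and the protocol's Analysis Population section:

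1. Define the primary efficacy set as all randomized subjects who received at least one infusion, active or placebo, analysed as randomized, with events counted through Week 26.
2. State how subjects lost before Week 26 are handled: for example, the planned Kaplan-Meier analysis with censoring, plus a best/worst-case or tipping-point analysis for the missing binary outcomes.
3. Keep the five-infusion set as a supportive per-protocol analysis, and state whether an infusion outside ±4 days counts as received for that set.
4. Run the sensitivity ANCOVA on whichever set is not used for the main analysis.
5. Reconcile SAP 6.1 with 5.5 and 7.1.3, so that one population is named for the primary test.
6. Date the amendment before unblinding, and disclose any earlier interim look, which the protocol allows the sponsor at any time.

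The cost is a protocol and SAP amendment. No clinical rule changes and no new data are needed, because the protocol already follows consenting subjects who stop infusions to Week 26 for efficacy as well as safety. Some outcomes will still be missing: at the planned 15% drop-out, 0.15 × 53 is about 8 subjects, hence item 2. The downside is small: the estimate will include subjects who were not fully dosed, and the supportive set covers that question.

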5. CONSIDERATIONS FOR DATA ANALYSES AND DATA HANDLING CONVENTIONS

5.1 Study Treatment & Sub-group Display Descriptors

Treatment Group Descriptions		
Protocol treatment arm	Data Displays for Reporting	
Treatment Arm	Treatment Arm	Order in TLF
Arm 1 (allogeneic HB-adMSCs 200MM)	aHB-adMSCs 200MM	1
Arm 2 (allogeneic HB-adMSCs 100MM)	aHB-adMSCs 100MM	2
Arm 3 (allogeneic HB-adMSCs 50MM)	aHB-adMSCs 50MM	3
Arm 4 (Placebo)	Placebo	4

Treatment comparisons will be displayed as follows using the descriptors as specified in the statistical analysis:

1. HB-adMSCs 200MM vs Placebo
2. HB-adMSCs 100MM vs Placebo
3. HB-adMSCs 50MM vs Placebo

5.2 Baseline Definitions

For all endpoints, the baseline value will be the latest pre-treatment assessment visit with a non-missing value. i.e., If an assessment has been made both at screening visit (Visit 1) and Week 0 infusion 1 visit (Visit 2), the value from the Week 0 visit is used as the baseline value. If the value measured at the randomisation visit is missing and the assessment also has been made at screening, then the screening value is used as the baseline value.

Unless otherwise stated, if baseline data is missing no derivation will be performed and baseline will be set to missing.

5.2.1 Change from Baseline

Definition	Reporting Details
Change from Baseline	= Post-Dose Visit Value – Baseline
% Change from Baseline	= 100 x [(Post-Dose Visit Value – Baseline) / Baseline]

NOTES:

- The baseline will be displayed along with Visit name on all summary displays.

5.3 Examination of Covariates, Other Strata and Subgroups

5.3.1 Covariates and Other Strata

Baseline will be included as a covariate in the efficacy analyses, wherever applicable.

Protocol Number: HBCOVID02
Hope Biosciences
Statistical Analysis Plan

Confidential

Date: 14-Oct-2021
Version: 1.0
Status: Final

5.3.2 Examination of subgroups

No subgroup analysis planned.

5.4 Multiple Comparisons and Multiplicity

The primary comparison of interest is the overall comparison between HB-adMSCs treatments and Placebo for the primary endpoint, incidence of the hospitalizations due to COVID-19 symptoms and incidence of the COVID-19 symptoms, so multiplicity adjustment is not needed. However, for exploratory purposes we perform a pair-wise comparison will done and results from following paired comparisons will be displayed to find the paired wise differences,

1. HB-adMSCs 200MM vs Placebo
2. HB-adMSCs 100MM vs Placebo
3. HB-adMSCs 50MM vs Placebo

We do statistical analysis for the primary endpoints and secondary outcomes as exploratory and test the outcome using $\alpha = 0.05$.

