7.1.2. Summary Measure

Binomial proportions difference between treatments.

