7.1.4. Statistical Analyses / Methods

Details of the planned displays are provided in Appendix 5: List of Data Displays.

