7.1.4.1. Statistical Methodology Specification

Incidence of Hospitalizations due to COVID-19 symptoms:

The primary endpoint analysis is the comparison between HB-adMSCs treatments vs Placebo are described in this table.

Primary endpoint will be analysed using the two sample Binomial proportion model for the comparison of HB-adMSCs 200MM vs. Placebo, HB-adMSCs 100MM vs. Placebo and HB-adMSCs 50MM vs. Placebo to test the the significance of the effects of the treatment.

Incidence of COVID-19 symptoms:

The primary endpoint analysis is the comparison between HB-adMSCs treatments vs Placebo are described in this table.

Primary endpoint will be analysed using the two sample Binomial proportion model for the comparison of HB-adMSCs 200MM vs. Placebo, HB-adMSCs 100MM vs. Placebo and HB-adMSCs 50MM vs. Placebo to test the the significance of the effects of the treatment.

Protocol Number: HBCOVID02
Hope Biosciences
Statistical Analysis Plan

Confidential

Date: 14-Oct-2021
Version: 1.0
Status: Final

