7.2.4.1. Statistical Methodology Specification

Change from baseline to Week 26 of treatment:

The secondary endpoint analysis is the overall treatment comparison between HB-adMSCs treatments and placebo. A pair-wise comparison of HB-adMSCs 200MM vs Placebo, HB-adMSCs 100MM vs Placebo and HB-adMSCs 50MM vs Placebo are also described in this table.

Secondary endpoint will be analysed using the standard ANCOVA model followed by Tukey's multiple comparison test to test the the significance of the effects of the treatment. The model includes treatment as fixed factor and the baseline value as a covariate.

Change from baseline to Week 14 end of infusion treatment:

The secondary endpoint analysis is the overall treatment comparison between HB-adMSCs treatments and placebo after Week 14 of infusion. A pair-wise comparison of HB-adMSCs 200MM vs Placebo, HB-adMSCs 100MM vs Placebo and HB-adMSCs 50MM vs Placebo are also described in this table.

Secondary endpoint will be analysed using the standard ANCOVA model followed by Tukey's multiple comparison test to test the the significance of the effects of the

Protocol Number: HBCOVID02
Hope Biosciences
Statistical Analysis Plan

Confidential

Date: 14-Oct-2021
Version: 1.0
Status: Final

treatment. The model includes treatment as fixed factor and the baseline value as a covariate.

Sensitivity/supportive analysis model

Change from baseline values of treatment will be analysed using the standard ANCOVA model based on efficacy analysis set followed by Tukey's multiple comparison test to test the the significance of the effects of the treatment. The model includes treatment as fixed factor and the baseline value as a covariate. A pair-wise comparison of HB-adMSCs 200MM vs Placebo, HB-adMSCs 100MM vs Placebo and HB-adMSCs 50MM vs Placebo are also described in this table for secundar endpoints.

A repeated measurements analysis (RMA) of value and change from baseline over Week 26 of treatment will be performed on the efficacy analysis sets, followed by Tukey's multiple comparison test to test the the significance of the effects of the treatment.

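### The SAP names the overall HB-adMSCs vs placebo comparison as primary but ties the binomial test only to the three dose pairs, and its reason for no multiplicity adjustment leaves the two primary endpoints without a success rule

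*SAP*

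**What the plan says.** SAP 2.3 sets two primary null hypotheses, one for hospitalization and one for symptoms. Each compares HB-adMSCs with placebo, two-sided at 5%; comparisons of individual doses with placebo come as an addition.

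SAP 5.4 names the overall comparison as the one of primary interest, for "incidence of the hospitalizations due to COVID-19 symptoms and incidence of the COVID-19 symptoms, so multiplicity adjustment is not needed". It then lists the three dose-vs-placebo comparisons as exploratory. Its last sentence describes the analyses of primary and secondary endpoints alike as exploratory, tested at 0.05.

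SAP 7.1.4.1 begins each endpoint with "The primary endpoint analysis is the comparison between HB-adMSCs treatments vs Placebo are described in this table". The only method sentence that follows, given once per endpoint, is "Primary endpoint will be analysed using the two sample Binomial proportion model for the comparison of HB-adMSCs 200MM vs. Placebo, HB-adMSCs 100MM vs. Placebo", continuing with 50MM vs placebo. It states no pooled test and does not call the pairs exploratory.

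Elsewhere the test is named without its groups. SAP 5.5 says "p-value will be displayed using two-sample binomial proportion test", SAP 6.1 says "A two sample binomial test will be applied for primary endpoints to calculate p-value comparing binomial proportions", and the summary measure in SAP 7.1.2 is "Binomial proportions difference between treatments".

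**The concern.** There are two gaps.

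- **Which comparison is tested.** The section a programmer would work from does not carry out the comparison that 5.4 and 2.3 call primary. Taken literally, it produces 3 doses × 2 endpoints = 6 unadjusted tests under the heading of the primary analysis.
- **What counts as success.** Using one overall comparison is a sound reason not to adjust across doses. It is no reason not to adjust across two endpoints, each with its own 5% test. Without a rule, a result on either endpoint could be presented as success.

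If comparison, endpoint rule and form of test all stay open, each could be settled after results are seen. The Protocol's Interim Analysis section lets the sponsor analyse efficacy data at any time, which makes this more than a formality.

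**Working it through.** **1. The sections side by side**

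| SAP section | Comparison for the primary endpoints | Status of the dose pairs |
|---|---|---|
| 2.3 | HB-adMSCs vs placebo | additional |
| 5.4 | overall HB-adMSCs vs placebo | exploratory |
| 5.5, 6.1 | groups not named | not tied to this test |
| 7.1.4.1 | lead-in: HB-adMSCs vs placebo; method: three dose pairs | no label |

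For the secondary endpoints, 7.2.4.1 is explicit: "The secondary endpoint analysis is the overall treatment comparison between HB-adMSCs treatments and placebo", with the dose pairs added afterwards. The primary section has no matching sentence.

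**2. Inputs**

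The plan has no figure to reproduce. It gives no familywise level, power or event rate, and the Protocol bases the 53 patients on numbers banked or registered to bank.

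- Alpha: 0.05 two-sided per endpoint (SAP 2.3).
- Allocation: 3:1 (SAP 2.2). 53 × 3/4 = 39.75 and 53/4 = 13.25, so about 40 vs 13.
- Drop-out: 15% (Protocol synopsis). 53 × 0.85 = 45.05, so about 45, or 34 vs 11 at 3:1.
- Assumed, because the documents give no rates: symptom risk 5–50% in 5-point steps (10 values); hospitalized share of symptomatic subjects 20–50% in 10-point steps (4 values); hospitalization only among symptomatic subjects; equal drop-out. That makes 10 × 4 = 40 settings.

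**3. Nominal benchmark**

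For two independent tests, 1 − (1 − 0.05)² = 0.0975. The upper bound is 0.05 + 0.05 = 0.10. The actual rate can be lower because the endpoints are correlated and small-sample binomial tests are discrete.

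**4. Exact null error of the two overall tests**

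For each setting, the joint null distribution of symptom and hospitalization counts in both groups was enumerated in full, and the probability of every rejecting outcome was summed. P(either) = P(symptoms rejects) + P(hospitalization rejects) − P(both reject). Ranges are over the 40 settings.

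| Rule | 40 vs 13, pooled z | 40 vs 13, Fisher | 34 vs 11, pooled z | 34 vs 11, Fisher |
|---|---|---|---|---|
| Symptoms test alone | 2.6–5.5% | 1.1–3.3% | 2.7–5.6% | 0.8–3.6% |
| Either endpoint at 5% | 2.9–9.3% | 1.1–5.2% | 2.9–9.3% | 0.8–6.3% |
| Settings above 5% (either) | 32 of 40 | 4 of 40 | 35 of 40 | 17 of 40 |
| Holm, any rejection | 2.8–4.8% | 0.4–2.7% | 2.5–4.7% | 0.4–2.5% |
| Both required (maximum) | 1.2% | 0.6% | 1.3% | 0.7% |

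**5. The form of the test can decide the result**

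Take 0/40 vs 2/13.

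- Pooled z: pooled proportion 2/53 = 0.0377; standard error √[0.0377 × 0.9623 × (1/40 + 1/13)] = 0.0608; z = 0.1538/0.0608 = 2.53; p = 0.011.
- Fisher: (13 × 12)/(53 × 52) = 156/2756; p = 0.057.

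For 0/34 vs 2/11 the p-values are 0.011 and 0.056.

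**6. The literal reading of 7.1.4.1**

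The chance of at least one false positive among the six dose tests, assuming equal arms, is 0.8–25.8% (pooled z) or 0.1–10.9% (Fisher) at 13 per arm. At 11 per arm it is 0.4–19.9% or 0.03–7.3%. These figures apply only if 7.1.4.1 overrides 5.4.

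**The case against.** The best defence is that the SAP, read as a whole, already settles the hierarchy. Sections 5.4 and 2.3 both put the overall comparison first, the lead-in to 7.1.4.1 agrees, and the three-pair list recurs in 5.1 and 5.5 as display wording. On that view one sentence is missing. The displays might also supply it: 7.1.4 states "Details of the planned displays are provided in Appendix 5: List of Data Displays", but neither that appendix nor the table mentioned in 7.1.4.1 is in the text available, so this could not be checked. On multiplicity, the last sentence of 5.4 calls the primary analyses exploratory, the sample size is not power-based, and with Fisher's test the excess is small and rests on assumed rates.

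Much of this stands. The overall comparison is probably what was meant, so the six-test figures are not the expected outcome. Exploratory status would justify making no adjustment. With Fisher at 40 vs 13, only 4 of 40 settings pass 5%.

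It does not close the gap. A list of displays would not remove the conflict between 5.4 and the method sentence in 7.1.4.1. Exploratory status is not the reason 5.4 gives, and it sits badly with the formal 5% hypotheses in 2.3.

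**Conclusion.** The concern holds, as something that should be fixed rather than a fatal flaw. The primary comparison named in 5.4 has no test attached in 7.1.4.1, and the argument against adjustment does not reach the two endpoints.

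If either endpoint counts as success, the error exceeds 5% by up to about 4 percentage points with the pooled z test and about 1 point with Fisher's. If both must succeed, or no confirmatory claim is made, there is no inflation to correct. These sizes depend on the assumed event rates, the nesting of hospitalization within symptoms and equal drop-out. The textual conflict depends on none of them.

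**What to change.** 1. In 7.1.4.1, state that all HB-adMSCs groups pooled vs placebo is the primary test for each endpoint, on the model of 7.2.4.1. Label the three dose comparisons exploratory, as 5.4 does. The proportion difference in 7.1.2 can stay as the summary measure.
2. Name the test in 7.1.4.1 and 5.5, for example Fisher's exact test or another small-sample method.
3. In 5.4, replace the no-adjustment statement with one rule for the two endpoints: a fixed sequence in an order the sponsor sets, Holm, or both required. Alternatively, declare the analysis exploratory in 2.3 and make no confirmatory significance claim; then no endpoint rule is needed.

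This changes SAP wording only and needs no new data or patients. The price is that per-dose results, and possibly one endpoint, can no longer be claimed as primary successes. Holm, a both-required rule or an exact test also costs some power. The SAP is already final, and the documents do not show whether data have been unblinded. If they have, the change must be disclosed as post hoc.
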